**Figure 1: Schematic representation of tiered immunogenicity testing**

**Table 1** provides clarification on when the reported value of a sample needs to be categorized as “negative”, “positive” or “missing” in each of the respective assays. Samples scoring negative in the ADA or mADA assay are not titrated and the respective log10(titer) is reported as <log10(Minimal required dilution [MRD]) with MRD=100, i.e. log10(titer) <2.00. The latter will not to be included in descriptive statistics on titers; but they will be included in the individual line plot, set arbitrarily to 1.80. Similarly, NAb negative results should not be included in descriptive statistics on response ratios, but will be included in the individual line plot, set arbitrarily to 1.00.

**Table 1: Reported values in each assay and corresponding data interpretation**

Reported value				Data interpretation
ADA: log10(titer)	mADA: log10(titer)	NAb data from parent trial: neutralizing response 	NAb data C203 post-baseline visits  : response ratio	
“< 2.00”	“< 2.00”	“Y”	Numeric value > CP 	NEGATIVE (NEG) (ISORRES)
Numeric value ≥ 2.00	Numeric value ≥ 2.00	“N”	Numeric value ≤ CP 	POSITIVE (POS) (ISORRES)
“NA” or “NR”	“NA” or “NR”	“NA” or “NR”	“NA” or “NR”	MISSING (COVAL)

 Parent trial screening and baseline visit as well as OLE baseline visit (corresponding to w24/w12 for C201/C202 respectively)

 NAb results reporting strategy has been adapted for study C203 compared to parent trial: NAb data are reported as response ratios, in contrast to C201/C202 results, which were reported as Y/N in the clinical database

 CP will be reported along with actual sample results

The immunogenicity status prior to drug administration will be derived from the parent trial (ALX0061-C201 or ALX0061-202) screening and baseline sample results (see further). The TE/post-dose response will be evaluated based on samples collected within ALX0061-C203 (OLE) at following timepoints according to schedule of assessment: Week 12, Week 24, Week 36, Week 48, Week 60, Week 72, Week 84, Week 96, Week 104 and

FU or ET visit. In all immunogenicity TFLs organized per timepoint, both parent screening & baseline as well as Week 0 need to be included.

## 9.2 Missing results and data imputation

The mADA assay will only be performed on a subset of samples ('Pre-Ab Pos – Equivocal'). In case no mADA results are reported for a given subject, the corresponding fields in the listing will remain empty and no data imputation is to be done.

The NAb assay will only be performed on a subset of samples (ADA positive samples). In case no NAb results are reported (empty field), the following imputations will be made (imputed values will be followed by “\*\*” in listings):

- No NAb record and corresponding ADA result NEGATIVE: these samples will be considered NEGATIVE and should appear as “NEG\*\*” in listings
- No NAb record and corresponding ADA result Not Analyzed (NA): these samples will be considered “NA” and should appear as “NA\*\*” in listings
- No NAb record and corresponding ADA result POSITIVE or No Result (NR): these samples will be considered “NR” and should appear as “NR\*\*” in listings

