### 3.2 Sample Size

This is an extension study and is not set by statistical power. Subjects who have completed the Week 24 (study ALX0061-C201) or Week 12 (study ALX0061-C202) assessment visit in one of the preceding Phase IIb studies with ALX-0061, and who are qualified for this study per inclusion/exclusion criteria, will be invited to participate in the extension study. Up to a maximum of approximately 501 subjects are planned to participate in this OLE study.

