## 9 ANALYSIS OF IMMUNOGENICITY

### 9.1 Available parameters

[figure not shown]
Immunogenicity is assessed via a tiered sample analysis approach (illustrated in Figure 1). In a first step all samples will be analyzed in the conventional anti-drug antibody (ADA) assay and only samples from subjects classified as 'Pre-Ab Pos – Equivocal' will be further analyzed in the mADA assay. This assay is a characterization assay and has been developed to enable detection of TE ADA in presence of (high) pre-existing antibody (pre-Ab) levels. Furthermore, positive ADA samples will be evaluated for their neutralizing potential in the neutralizing antibody (NAb) assay.

As such, the available parameters per sample are:

- ADA log10(titer) (no data imputation)
- mADA log10(titer) (for subset of subjects only, no data imputation)
- NAb normalized response (for subset of samples only, data imputation required for ADA negative samples)

Additional provided information needed for data interpretation is:

- ADA Minimum Significance Ratio (MSR): MSR is an assay parameter reflecting precision of titer assessments and is needed to interpret the treatment emergent (TE) response for subjects presenting with pre-Ab. In such cases, pre- and post-dose titers will be compared. The titer is considered to be significantly increased post-dose, if the highest post-dose titer compared to the highest pre-dose titer is higher than the MSR value. The increase of the log10(titer) post- versus pre-dose should be  $> \log_{10}(\text{MSR})$ .
- mADA MSR: MSR value determined in the mADA assay, similar application as described above, but applied to mADA titers.
- NAb assay cutpoint (CP): cut-off value to determine if a sample is negative or positive. Since the NAb assay is an inhibition assay, samples equal to or below the CP will be considered positive.

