### 9.3.4 NAb subject class

All available NAb assay results (\*) (positive or (imputed) negative) per subject will be evaluated and subjects will be classified based on a combined statement on pre-dose status (pre-dose neg or pre-dose pos, to be derived from parent trial) and the post-dose response (negative, positive or inconclusive) as outlined in [Table 5](#).

(\*) Note that for the pre-dose Nab results (screening and baseline) from the parent trials (ALX0061-C201 or ALX0061-C202) 'Y' (Yes) should be imputed to POS and 'N' (No) should be imputed to NEG.

For each subject, one NAb subject classification is to be determined. This implies that in the listing this will be identical for all NAb visits of the given subject. For subjects with no positive ADA samples, the NAb results were imputed as "NEG\*", and the NAb subject class will be "PRE-DOSE NEG - NEG ON TREATMENT". The latter also has to appear in the Listing.

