**Table 5: NAb subject classification**

NAb subject class	Evaluation based on all NAb assay results (titer) of the respective subject	
	Pre-dose status evaluated on screening and baseline of parent trial	Response on treatment evaluated based on Week 12, Week 24, Week 36, Week 48, Week 60, Week 72, Week 84, Week 96, Week 104 and FU or ET visit
PRE-DOSE NEG - NEG ON TREATMENT	All pre-dose samples negative (reported or imputed)	All post-dose samples are negative (reported or imputed)
PRE-DOSE NEG - POS ON TREATMENT	All pre-dose samples negative (reported or imputed)	At least one positive sample(s) post-dose
PRE-DOSE POS - NEG ON TREATMENT	One or more of the pre-dose samples is positive	All post-dose samples are negative (reported or imputed)
PRE-DOSE POS - POS ON TREATMENT	One or more of the pre-dose samples is positive	At least one positive sample(s) post-dose
PRE-DOSE NEG - INCONCLUSIVE	All pre-dose samples negative (reported or imputed)	All post-dose samples(/results) are missing
PRE-DOSE POS - INCONCLUSIVE	One or more of the pre-dose samples is positive	All post-dose samples(/results) are missing
MISSING	No pre-dose (and/or post-dose) samples are available	No pre-dose (and/or post-dose) samples are available

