#### **9.4.6 ADA and NAb incidence over time**

For ADA and NAb data, incidence of positive samples over time will be calculated. Positivity needs to be deducted based on reported titer values (ADA) or response ratio (NAb), as clarified in [Table 1](#). Incidence calculation should account for subject drop-out: for each visit, the number of positive samples is divided by the available results for the given visit (positive + negative samples (reported and/or imputed), excluding missing values (NA & NR)). The latter should be clarified in a footnote of the concerning tables.

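### Missing NAb results can arise only on ADA-positive or unresolved samples: per-visit NAb incidence drops these but keeps every imputed negative, and Table 5 has no class for subjects with both negative and NR samples

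*SAP*

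**What the plan says.** SAP 9.1 plans that "positive ADA samples will be evaluated for their neutralizing potential in the neutralizing antibody (NAb) assay", and 9.2 confirms that "The NAb assay will only be performed on a subset of samples (ADA positive samples"). Section 9.2 then covers samples with no NAb record in three ways:

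- ADA-negative: "No NAb record and corresponding ADA result NEGATIVE: these samples will be considered NEGATIVE".
- ADA not analyzed: NA.
- ADA-positive, or ADA with no result: "No NAb record and corresponding ADA result POSITIVE or No Result (NR): these samples will be considered" NR.

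Table 1 reads both NA and NR as missing.

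For incidence over time, 9.4.6 divides positive samples by positive plus negative samples, whether reported or imputed, "excluding missing values (NA & NR"). Table 14.3.4.8 repeats the exclusion.

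For subject classes, 9.3 works from whatever data are available and makes a NAb class mandatory. Section 9.3.4 evaluates the available results ("positive or (imputed) negative) per subject will be evaluated and subjects will be classified based on a combined statement on pre-dose status" and post-dose response). Table 5 assigns NEG ON TREATMENT when "All post-dose samples are negative (reported or imputed"), and INCONCLUSIVE only when every post-dose result is missing. Section 9.4.4 removes only MISSING subjects from the denominator, so INCONCLUSIVE subjects stay in it.

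**The concern.** Once ADA-negative samples are imputed, the only samples that can lack a NAb result are ADA-positive ones and those whose ADA status is itself NA or NR. Missingness is thus tied by rule to the one feature that makes a positive NAb result possible. Discarding those samples while counting every ADA-negative sample as a negative dilutes the rate. Nothing in the SAP ties missing ADA results to the outcome in this way, so ADA incidence is not affected.

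The subject classes have a related gap. Take a subject with one ADA-positive post-dose sample that has no NAb result and ADA-negative samples at the other visits. The only sample that could have been NAb-positive is unknown, yet the available results are all imputed negatives. The same can happen at parent-trial screening and baseline, where a pre-existing NAb could later be counted as new on treatment. NAb classification is one of the two immunogenicity endpoints in SAP 3.3.

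**Working it through.** The documents state no NAb figure, so there is nothing to reproduce, and power inputs do not apply ("This is an extension study and is not set by statistical power"). The rules come from SAP 9.2, 9.3.4, Table 5, 9.4.4 and 9.4.6. Three quantities are not in the documents and are assumed: p, the ADA-positive share of samples at a visit; q, the NAb-positive share among ADA-positive samples; and f, the share of ADA-positive samples with no NAb result. Samples with ADA status NA or NR are set aside.

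**Per visit, missing at random among ADA-positives**

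- True rate = p·q.
- SAP rate = p·q·(1−f) / (1−p·f).
- Ratio = (1−f) / (1−p·f), which is below 1 whenever f > 0 and p < 1. It does not depend on q.

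| f | ratio, p = 0.2 | ratio, p = 0.4 |
|---|---|---|
| 0 | 1 | 1 |
| 2% | 0.98/0.996 = 0.984 | 0.98/0.992 = 0.988 |
| 5% | 0.95/0.99 = 0.960 | 0.95/0.98 = 0.969 |
| 10% | 0.90/0.98 = 0.918 | 0.90/0.96 = 0.938 |
| 20% | 0.80/0.96 = 0.833 | 0.80/0.92 = 0.870 |

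**Illustration with assumed counts.** Of 100 samples, 30 are ADA-positive. Ten of these have no NAb result, and 10 of the 20 tested are NAb-positive.

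- SAP rule: 10/(100−10) = 11.1%.
- Stratified on ADA status: 30% × 10/20 = 15.0%.
- Untested all negative: 10/100 = 10.0%. Untested all positive: 20/100 = 20.0%.

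**Direction without missing at random.** If a fraction x of the 10 untested samples is truly positive, the true rate is (10 + 10x)/100. This exceeds 11.1% exactly when x exceeds 11.1%, the reported rate itself. Missing at random gives x = 50% here, well above that.

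**Subject level, rules applied.** There are 10 post-dose samples: nine visits and the follow-up or early termination visit.

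| Untested ADA-positive / ADA-negative | Available-results reading | Literal Table 5 |
|---|---|---|
| 1 / 9 | NEG ON TREATMENT | no class |
| 5 / 5 | NEG ON TREATMENT | no class |
| 9 / 1 | NEG ON TREATMENT | no class |
| 10 / 0 | INCONCLUSIVE | INCONCLUSIVE |

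For a subject with a single ADA-positive sample, the chance of a wrong negative class is f·q. With f = 0.2 and q = 0.4 it is 8%.

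**Subject level, simulation.** This used 200,000 subjects on the available-results reading. It assumed that 30% of subjects can become ADA-positive and that half of those are NAb-positive, with 33% of ADA-positive samples untested at random.

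- ADA positivity at about 20% of visits: true subject-level incidence 13.4%, SAP 11.5%, with 1.9% of all subjects true positives called negative.
- ADA positivity at every visit: 15.0% against 15.0%.

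The subject-level effect therefore depends on ADA positivity being intermittent, or on missingness clustering within subjects.

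**The case against.** The strongest reply is that this is a fallback rule. Section 9.1 sends positive ADA samples to the NAb assay without naming a subset, so f should be near zero and the bias with it. Imputed values are marked in the listings, 9.4.6 requires a footnote on the denominator, the analyses are descriptive, and no decision rests on NAb incidence. All of this is fair and limits the size. It does not remove the point: 9.2 provides for an ADA-positive sample with no NAb record, and the later sections do not carry that case through. The planned tables do not show how many such samples there are.

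Four stronger readings are tempting and are not supported.

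- A reader might infer that untested ADA-positive subjects are reported as NAb-negative in general. The sample is set to NR, not negative, and a subject with no post-dose result is properly INCONCLUSIVE. Only the mixed case is affected. Its negative class follows from the available-results wording of 9.3 and 9.3.4, while Table 5 read literally leaves it unclassified.
- A reader might infer that downward bias is certain. It needs untested ADA-positive samples to be positive more often than the reported rate, and some missing results belong to samples of unresolved ADA status.
- A reader might infer that a subject with one untested ADA-positive sample is wrongly called negative with probability f. The probability is f·q.
- A reader might infer that recoding corrects the positive total. Set 11 counts only NAb-positive subjects, and INCONCLUSIVE subjects stay in the denominator, so set 11 does not move.

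An ADA-stratified rate also rests on missing at random, which cannot be tested. That is a reason to show bounds beside it.

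**Conclusion.** The point holds in a limited form. The per-visit rule gives a diluted NAb incidence whenever ADA-positive samples lack a NAb result and their positivity exceeds the reported all-sample rate. Under missing at random among ADA-positives, with p between 0.2 and 0.4, the relative shortfall is 1.2 to 1.6% at f = 2% and 6 to 8% at f = 10%. It is zero if every ADA-positive sample is tested. Both p and f are assumptions, so the actual size cannot be determined from the documents.

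At subject level, the class of a mixed negative and NR subject is either negative without adequate evidence or undefined. The negative reading inflates set 10 (total negative on treatment). The same gap pre-dose can distort sets 8, 9, 13 and 14. The change is worth making before database lock because it is cheap and concerns a listed endpoint, but it is a correction of moderate weight.

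**What to change.** 1. In 9.3.4 and Table 5, class a subject as INCONCLUSIVE on treatment if any post-dose ADA-positive sample has no NAb result and no post-dose sample is NAb-positive. Add an explicit pre-dose unknown class for the same situation at screening and baseline. Keep it out of PRE-DOSE NEG and out of set 13, and state whether these subjects count in the 9.4.4 denominator.
2. In 9.4.6 and Table 14.3.4.8, print the number of ADA-positive samples without a NAb result at each visit. Show NAb incidence among NAb-tested ADA-positive samples, and the ADA-stratified overall rate (ADA-positive share × NAb-positive share among those tested). Add bounds that set the untested ADA-positive samples all negative and all positive.

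The cost is SAP wording and a small extra derivation, with no new samples or assays. A few subjects would move from negative to inconclusive, which is a slightly less favourable display.

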## 9.3 Subject classifications (derived parameters)

Subject classification on immunogenicity results (ADA, mADA and NAb) will be based on the assay results (titers or response ratios outlined in [9.1](#)). Subject classifications will be attributed based on all available data for each subject.

One subject will either have three or four subject classifications:

- an ADA subject classification (mandatory)
- a mADA subject classification (optional, only for subjects with ADA classification “Pre-Ab positive – Equivocal”)
- an overall subject classification (combining results of ADA and mADA analysis)
- a NAb subject classification (mandatory, derived from reported and/or imputed results)

Subjects will be classified based on their pre-dose status (i.e. screening and baseline) and treatment-emergent (TE) status (post-dose response). The immunogenicity status prior to drug administration will be derived from the parent trial (ALX0061-C201 or ALX0061-C202) screening and baseline sample results. The TE/post-dose response will be evaluated based on samples collected within ALX0061-C203 at following time points: Week 12, Week 24, Week 36, Week 48, Week 60, Week 72, Week 84, Week 96, Week 104 and FU or ET visit.

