**Table 2: ADA subject classification**

ADA subject class	Evaluation based on all ADA assay results (titer) of the respective subject	
	Pre-Ab status evaluated on screening and baseline sample of parent trial	TE ADA Response evaluated based on Week 12, Week 24, Week 36, Week 48, Week 60, Week 72, Week 84, Week 96, Week 104 and FU or ET visit
PRE-AB NEG - TE ADA NEG	All pre-dose samples negative	All post-dose samples ADA negative
PRE-AB NEG - TE ADA POS	All pre-dose samples negative	At least one positive ADA sample(s) post-dose
PRE-AB NEG - TE ADA INCONCLUSIVE	All pre-dose samples negative	All post-dose samples(/results) are missing
PRE-AB POS - TE ADA NEG	One or more of the pre-dose samples is positive	All post-dose samples are ADA negative
PRE-AB POS - TE ADA POS	One or more of the pre-dose samples is positive	Significant increase in titer post-dose versus pre-dose*
PRE-AB POS - EQ	One or more of the pre-dose samples is positive	Positive ADA sample(s) post-dose and no significant increase in titer post-dose versus pre-dose*
PRE-AB POS - TE ADA INCONCLUSIVE	One or more of the pre-dose samples is positive	All post-dose samples(/results) are missing
MISSING	No pre-dose samples are available	N/A

\* The titer is considered to be significantly increased post-dose, if the highest post-dose titer compared to the highest pre-dose titer is higher than the ADA MSR value: the increase of the  $\log_{10}(\text{titer})$  post- versus pre-dose should be  $> \log_{10}(\text{MSR})$ .

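### The ADA, mADA and NAb subject classes place the Week 0 sample in neither the pre-dose nor the post-dose window, which can bias treatment-emergent incidence down in the parent ALX-0061 arms and up in the ex-placebo arm

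*SAP*

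**What the plan says.** SAP 9.3 sets two windows that are the same for every treatment group. Pre-dose: "The immunogenicity status prior to drug administration will be derived from the parent trial (ALX0061-C201 or ALX0061-C202) screening and baseline sample results". Post-dose: "The TE/post-dose response will be evaluated based on samples collected within ALX0061-C203 at following time points", namely Weeks 12, 24, 36 and so on to Week 104, plus the follow-up or early termination visit. SAP 9.1 states the same rule, and the column headers of Table 2 (ADA), Table 3 (mADA) and Table 5 (NAb) build it in.

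Footnote 1 to Table 1 identifies the Week 0 sample by grouping together "Parent trial screening and baseline visit as well as OLE baseline visit (corresponding to w24/w12 for C201/C202 respectively". Week 0 is thus the final parent-study sample. It is kept in the displays: "In all immunogenicity TFLs organized per timepoint, both parent screening & baseline as well as Week 0 need to be included".

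Two general statements sit beside these windows. SAP 9.3 says: "Subject classifications will be attributed based on all available data for each subject". The header of Table 2 reads: "Evaluation based on all ADA assay results (titer) of the respective subject". SAP section 11, on changes from the protocol, does not mention the choice of windows.

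**The concern.** Week 0 means different things in different arms, and the classification uses it in none of them. SAP 7.1 states that dosing continues without interruption from the parent study, so in the parent ALX-0061 arms Week 0 is an on-treatment sample. Footnote K of the schedule of assessments says immunogenicity samples are drawn before dosing. In the C201 placebo group Week 0 is therefore the last sample before the first ALX-0061 dose.

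The resulting TE incidence has no clean interpretation. It is not cumulative from first exposure, because antibody seen only up to Week 0 is lost. Nor is it incidence arising in the extension, because antibody that arose in the parent study and persisted is counted. The two errors run in opposite directions across groups that the tables show side by side. The classes feed the incidences in SAP 9.4.1 to 9.4.4 (Tables 14.3.4.1 to 14.3.4.4) and the injection-site and hypersensitivity cross-tables in 9.4.5 (Tables 14.3.4.5 and 14.3.4.6). Antibody incidence is one of the safety analyses named in protocol 3.6.6.

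**Working it through.** **The plan's own count.** Protocol Table 2 (blood volumes) gives 10 immunogenicity samples of 7 mL, or 70 mL. The nine visits from Week 12 to Week 104 plus Follow-up make 10, and 10 x 7 = 70 mL, so the figure reproduces. The TE list therefore matches the samples newly drawn in C203. Week 0 is left out of the count because it is a parent-study draw.

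**Time before the first countable sample in the ALX-0061 arms, from parent Week 0.**
- C201: 24 + 12 = 36 weeks, out of 24 + 104 = 128 to OLE Week 104 (28%).
- C202: 12 + 12 = 24 weeks, out of 12 + 104 = 116 (21%).

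**Applying the class rules.** Each result pattern was classed twice: by the SAP windows, and with Week 0 counted as post-dose (ALX-0061 arms) or pre-dose (ex-placebo). Numbers are log10 titers. For pre-Ab positive subjects Table 2 requires an increase above log10(MSR). The MSR is not given; the examples assume MSR = 3, so the threshold is 0.48.

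| Arm | Screening/baseline | Week 0 | Week 12 onward | SAP class | Week 0 counted |
|---|---|---|---|---|---|
| ALX-0061 | neg | pos | neg | PRE-AB NEG - TE ADA NEG | PRE-AB NEG - TE ADA POS |
| ALX-0061 | neg | pos | none | PRE-AB NEG - TE ADA INCONCLUSIVE | PRE-AB NEG - TE ADA POS |
| ALX-0061 | 2.0 | 3.0 | 2.0 | PRE-AB POS - EQ | PRE-AB POS - TE ADA POS |
| ALX-0061 | 2.0 | 2.0 | neg | PRE-AB POS - TE ADA NEG | PRE-AB POS - EQ |
| ALX-0061 | neg | pos | pos | PRE-AB NEG - TE ADA POS | unchanged |
| Ex-placebo | neg | 2.0 | 2.0 | PRE-AB NEG - TE ADA POS | PRE-AB POS - EQ |
| Ex-placebo | neg | 2.0 | 3.0 | PRE-AB NEG - TE ADA POS | PRE-AB POS - TE ADA POS |
| Ex-placebo | neg | pos | neg | PRE-AB NEG - TE ADA NEG | PRE-AB POS - TE ADA NEG |

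**All patterns.** For ADA, with results negative, 2.0 or 3.0 (and post-dose also missing), there are 3 x 3 x 4 = 36 patterns. With MSR assumed at 2, 3 or 5, the class changes in 16 of 36 for the ALX-0061 arms and 9 of 36 for ex-placebo. With MSR 20 it changes in 15 and 8. For NAb there are 2 x 2 x 3 = 12 patterns, of which 6 and 3 change. These are counts of logical possibilities, not proportions of subjects.

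**Direction.** Where parent screening or baseline results exist, adding Week 0 to the post-dose set can only raise the highest post-dose result, so TE POS can gain subjects but not lose them. Adding it to the pre-dose set can only raise the highest pre-dose result, so TE POS can lose subjects but not gain them.

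**Size.** If a share u of an ALX-0061 arm is TE positive only when Week 0 counts, the SAP incidence is lower than the exposure-based one by exactly u. The documents give no value for u, and zero is possible.

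**The case against.** The strongest defence is that the windows are explicit, stated consistently in several places, and describe an extension-period analysis, much as SAP 5.4 restricts exposure to the OLE. On that view post-dose simply means what the column header lists, and the references to all available data mean all non-missing results. This has force against the charge of self-contradiction: a specific rule governs a general sentence, and the tension in wording is not the main point. It does not rescue the classification. An extension-only TE status would need Week 0 as its reference, whereas the SAP compares with status before any parent dosing.

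Other objections stand and limit the point.
- A reader might infer that the plan ignores Week 0 altogether. It does not. Week 0 appears in the incidence and titer tables over time, the individual plots and the full listing. It is missing only from the subject classes and what is built on them.
- A reader might infer that other parent on-treatment samples are also being discarded. The documents do not give the parent immunogenicity schedule, so such samples are not established. The Week 0 argument does not need them.
- Full loss from TE POS requires a negative result at every available later sample. The ex-placebo error requires negative screening and baseline samples, a first positive by parent Week 24 on placebo, and a further positive later. Both may be uncommon.
- Widening the ADA window has its own consequence. SAP 7.1 by default limits AE tables to events starting after the first C203 dose, so Tables 14.3.4.5 and 14.3.4.6 would cross a longer ADA period with a shorter AE period unless the periods are stated.
- The analysis is descriptive ("This is an extension study and is not set by statistical power"), so no test or sample size is affected.

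**Conclusion.** The point holds for the subject classes in Tables 2, 3 and 5 and for the incidences in 9.4.1 to 9.4.5. It rests on three things the documents state: dosing is uninterrupted for subjects already on ALX-0061, samples are taken before dosing, and Week 0 is listed in neither window. The ex-placebo part concerns one group, because SAP 4.2.2 lists a placebo origin for C201 only.

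The direction of possible bias is known: down in the ALX-0061 arms, up in the ex-placebo arm. The size is not, and it may be small. Only subjects whose Week 0 result changes their class are affected; a pre-Ab negative ALX-0061 subject whose antibody persists to Week 12 or later is still TE POS. It would be wrong to read the pattern counts, or any assumed rate of transient ADA, as an expected share of misclassified subjects, because the documents contain no ADA rates. The change is worth making before database lock, since it alters what a reported safety incidence means.

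**What to change.** In SAP Tables 2, 3 and 5, define the windows by parent treatment:
- Subjects randomized to ALX-0061 in the parent study: count Week 0 as post-dose, and add other parent on-treatment results only if they exist.
- C201 placebo group: count Week 0 as an additional pre-dose sample.
- Show a separately labelled C203-only row (Week 12 onward), so that the presently planned incidence remains visible.
- State in Tables 14.3.4.5 and 14.3.4.6 which ADA period and which AE period are crossed.

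The cost is mainly SAP wording and programming, as Week 0 results are already in the outputs. There are two further costs. Some subjects become newly PRE-AB POS - EQ; under SAP 9.1 and 9.3.2 they qualify for mADA testing, and without it Table 4 leaves them EQ, outside the TE POS total. The NAb coding must also be settled first: Table 1 puts a parent result of Y in the negative row and N in the positive row, while the note in SAP 9.3.4 maps Y to positive and N to negative. Week 0 NAb results carry this Y/N coding, so the two places must be reconciled before those results are used.
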